 517 bedtime), and as needed to calibrate the CGM. Additional
 518 fingersticks may be obtained, if desired.
- 519 • If a subject is a CGM-wearer at screening, the subject may continue to
 520 use the home CGM during blinded study CGM use.

521
 522 The screening visit and training session will last approximately 3 hours. This
 523 may be shorter depending on the amount of pre-screening that was performed
 524 and the subject’s prior knowledge of study devices.

525
 526 If the subject cannot schedule Visit 3 within 4 weeks of screening, the
 527 inclusion and exclusion criteria will be re-evaluated. The study physician will
 528 have the discretion to repeat any test as needed.

529
 530 **2. Visit 2: Screening 2 Visit**

531 After completion of 1 week of baseline blinded CGM use, the subject will return to have the
 532 Dexcom CGM and study glucometer downloaded to assess the subject’s baseline risk for
 533 hypoglycemia and evaluate the reliability of CGM data collection. The meter data will be

534 assessed for average SMBG/day and randomness of data. Subjects with average SMBG
535 <3.5/day and/or poor randomness of SMBG testing will be reminded of SMBG requirements
536 4-6 times daily (pre-meal, bedtime, before driving, before exercise, and as indicated).
537

538 In order to continue with the trial, the subject must have all of the following:

- 539 • Baseline LBGI >1.1 as assessed by the prior 1 week of blinded CGM data
- 540 • CGM must have been functional >80% of the time (i.e. >1600 CGM data
541 points/week).

542
543 CGM data collection period may be repeated. Eligible subjects will be scheduled for
544 Visit 3 within 3 weeks of Visit 2. Subjects will be randomized to experimental
545 treatment with the AP system+USS Virginia or control treatment with sensor-
546 augmented pump therapy. Groups will be matched for LBGI and pre-study CGM
547 use.
548

549 **Preparation for Visit 3:**

- 550 • All subjects will be given written instructions to bring their pump supplies,
551 glucometer supplies, CGM supplies, insulin and all of their current
552 medications (including aspirin or regular analgesics) with them for use during
553 the admission.
- 554 • These instructions will also advise the subject to contact the study team in the
555 event of a febrile or vomiting illness within 24 hours of the admission, so that
556 the admission can be rescheduled.
- 557 • The subject will be asked to avoid the need for a pump site change during Visit
558 3.

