 1894 Board (DSMB), or sponsor may decide to stop the trial or part of the trial at any time. In
 1895 this case, the Principal Investigator will promptly inform the subjects and assure
 1896 appropriate therapy and follow-up. Additionally the Principal Investigator will notify the
 1897 IRB and DSMB if the study is temporarily stopped. The pertinent regulatory authorities
 1898 will be informed according to national regulations. The DSMB will meet to determine if
 1899 changes to the protocol or system are needed prior to restarting the study and whether the
 1900 study may be restarted.

1901

1902 Early study stop will be documented and following information will be collected:

- 1903 > Date and cause of the ending
- 1904 > Description of any serious adverse event leading to the study ending

1905

1906 A subject who does not complete the at least 1 week of the study intervention may
 1907 be replaced. Available data will be exploited.

1908

1909 In the case of an unanticipated adverse device effects (UADE), the overall study may be
 1910 suspended while the problem is diagnosed and the PI investigates the UADE. If the PI
 1911 determines that the UADE poses an unreasonable risk to subjects, the study should be
 1912 suspended until this UADE can be resolved. If it cannot be resolved, the study should be
 1913 terminated. Termination should occur no later than 5 working days after PI makes the
 1914 decision. The result of the investigation and the PI’s decision to terminate the study shall
 1915 be reported the site IRB, and the FDA per 21CFR 812.46(b) (2). The DSMB must
 1916 determine if the UADE presents an unreasonable risk to subjects. If so, the DSMB must
 1917 ensure that all investigations, or parts of investigations presenting that risk, are terminated
 1918 as soon as possible but no later than 5 working days after the DSMB makes this
 1919 determination and no later than 15 working days after first receipt notice of the UADE.

1920

1921 The study may resume if the underlying problem can be corrected by a protocol or
 1922 system modification that will not invalidate the results obtained prior to suspension. The
 1923 IRB and DSMB will be notified if the study is stopped, and permission to resume will be
 1924 obtained from the FDA, DSMB and IRB prior to restarting.

1925

1926 **CATASTROPHIC EVENT PLAN**

1927 The Outpatient Emergency Plan will go into effect should a catastrophic event occur

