Serious, unexpected and related or possibly related adverse events	All Research Sites	Within 15 days after the Overall PI receives knowledge	IND/IDE Safety Report (Cover letter, copy of MedWatch/narrative)

		of the event.	
For Device Studies: Unanticipated adverse device effects (internal or external)	All Research Sites	Within 15 calendar days from the time the Overall PI receives knowledge of the event.	Letter to Participating PIs, Copy of MedWatch or narrative
Unanticipated Problem	All Research Sites	Within 15 calendar days from the time the Overall PI receives knowledge of the event.	Letter to Participating PIs, Copy of MedWatch or narrative

1942
1943

1944

J. ENDPOINTS

1945
1946
1947
1948
1949
1950
1951
1952
1953
1954
1955
1956

This study is a randomized, controlled trial involving subjects with type 1 diabetes to test the effectiveness of the Unified Safety System (USS) Virginia closed-loop in preventing hypoglycemia compared with sensor-augmented pump (SAP) therapy. We will also evaluate the effectiveness of the control system (USS Virginia) at improving hypoglycemia counterregulation, hypoglycemia awareness, and overall glycemic control compared with versus SAP. To achieve this goal, we will conduct pre- and post-intervention inpatient assessments of hypoglycemia counterregulation and symptom awareness. For the interventions, subjects randomized to USS Virginia will participate in two training visits at a monitored outpatient setting for the step-wise deployment of the AP system at home in Pump mode followed by 4 weeks using AP at home in Closed Loop mode running USS Virginia. Subjects randomized to sensor-augmented pump therapy will complete 5 weeks of CGM with the home pump.

1957
1958
1959
1960
1961
1962

The basic unit for analyses of hypoglycemia risk and occurrence is the glucose trace of an individual, i.e. a time-stamped series of CGM data recorded for each person. Summary characteristics and group-level analyses are derived after the individual traces are processed to produce meaningful individual markers of average glycemia and glucose variation.

1963
1964
1965

The following primary endpoint of reduction in hypoglycemia will be assessed by:
1. LBGI from CGM during 1 week of blinded use versus during the last week of

1966 intervention

1967

1968 The secondary endpoints of improvement in counterregulatory response to hypoglycemia and
 1969 hypoglycemia awareness at baseline versus follow-up will be assessed by:

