- 1970 1. Peak epinephrine
- 1971 2. Epinephrine AUC
- 1972 3. Epinephrine increase over baseline
- 1973 4. Hypoglycemia symptom ratings
- 1974 5. Clarke Hypoglycemia Perception Awareness score
- 1975 6. Fear of hypoglycemia scores

1976

1977 Additional secondary endpoints of reduction in hypoglycemia will be assessed by:

- 1978 1. CGM time <70 mg/dL and <50 mg/dL by retrofitted CGM and SMBG trace from 1
 1979 week of blinded use versus the last week of intervention
 - 1980 a. During 24 hours, and
 - 1981 b. Overnight (11PM – 7AM)

1982

1983 Additional secondary endpoints of improvement in glycemic control at baseline versus the
 1984 last week of intervention will be assessed by:

- 1985 1. Time within target (70-180 mg/dL) over a 24 hour period
- 1986 2. Time within target range of 80-140 mg/dL overnight (11PM – 7AM), and
- 1987 3. Distribution of wake-up glucose levels at 7AM

1988

1989 **K. SUCCESS CRITERIA / GOAL**

1990 As a general rule, a subject’s data will be considered useful for data analysis if the
 1991 subject completes at least 1 week of study intervention with USS Virginia+AP system or
 1992 SAP.

1993 **L. STATISTICAL ANALYSIS PLAN**

1994 Sample size determination is based on literature data (#3) and on results from our
 1995 previous studies of hypoglycemia unawareness (#4)(#5). We estimate, conservatively,
 1996 that the effect size of using the AP system+USS Virginia vs. CGM in terms of
 1997 restoration of epinephrine response will be moderate ~0.35. Power calculations assuming
 1998 $\alpha=0.05$, and power of 80% yield a required sample size of N=36 (using G*Power 3
 1999 software [#5]). With this sample size, the power for finding significant effects on
 2000 frequency and extent of hypoglycemia (Low BG Index [#6]) exceeds 0.9. Assuming a
 2001 proportion of noncompliance R=20% for Intention-to-Treat (ITT) analysis (#7), 44
 2002 completed subjects will adequately address the specific aims of this study. Per-protocol
 2003 analysis will also be performed. In order to achieve 44 completed subjects, up to 70

2004 subjects may sign consent given an expected screen failure, withdrawal and drop-out rate
2005 of ~40% due to the rigorous exclusion criteria and requirements imposed for the AP
2006 system use in the subject's local environment.
2007
2008

2009 REFERENCES

- 2010 #1 Diabetes Research in Children Network (DirecNet) Study Group, Tsalikian E,
2011 Tamborlane W, Xing D, Becker DM, Mauras N, Fiallo-Scharer R, Buckingham B,

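### The plan names an ITT analysis, but Sections K and I permit randomised subjects with under 1 week of intervention to be left out or replaced, and removal on device or task criteria is stated for the closed-loop arm only

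*Combined protocol and SAP*

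**What the plan says.** Section L (repeated in Section D) inflates the sample size for a "proportion of noncompliance R=20% for Intention-to-Treat (ITT) analysis (#7), 44" completed subjects, and adds that a per-protocol analysis will also be done. No section defines the ITT set.

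Section K, just above it, states as a general rule that a subject's data are useful for analysis if the "subject completes at least 1 week of study intervention with USS Virginia+AP system or" sensor-augmented pump therapy.

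Section I, under the rules for stopping the entire study, says: "A subject who does not complete the at least 1 week of the study intervention may" "be replaced. Available data will be exploited". It does not say in which analysis.

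Randomisation comes earlier. Section G.2 reads "Visit 3 within 3 weeks of Visit 2. Subjects will be randomized to experimental" or control treatment, and Section B also places it at Visit 2.

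The primary endpoint in Section J is "LBGI from CGM during 1 week of blinded use versus during the last week of" intervention.

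**The concern.** Randomisation protects the LBGI comparison only if subjects are counted in the arm to which they were allocated, whatever happens next. A rule that makes inclusion depend on a week of treatment uses an event after randomisation.

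The two arms do not reach that week by the same route. Control subjects go from Visit 3 straight to 5 weeks of CGM with their own pump, and no device-use, monitoring or task threshold for removing them is stated. Closed-loop subjects must pass several such thresholds. If those who fail differ in hypoglycaemia risk from those who pass, leaving them out shifts one arm's mean and not the other's.

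An analyst who follows Section L and one who follows Section K could analyse different subjects. For early stoppers they could also use different weeks, because the endpoint week is not tied to a scheduled week for subjects who do not finish.

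**Working it through.** **1. The plan's own figure.** Inputs from Section L: N = 36, R = 20%, result 44. 36 / (1 − 0.20) = 45; 36 × 1.20 = 43.2, rounded up to 44. So 44 reproduces, and 44 − 36 = 8 subjects is an allowance for noncompliers who are analysed. That points towards keeping them.

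**2. Which criteria can remove a subject after randomisation, and when.** Stops for pregnancy, glucocorticoids, repeated acetaminophen, serious events or persistent loss of contact can apply in either arm. The following are stated for the closed-loop arm only:

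| Criterion | Where stated | Timing against 1 week |
|---|---|---|
| Independent tasks after Visit 4 training | G.4, I | At the first Visit 4: below 1 week on any reading |
| Pump-mode use above 80% | G.5, I | At or after the end of the Pump-mode week |
| Remote monitoring at least 75% | G.5, I | As above |
| Independent tasks after Visit 5 training | G.6, I | Before closed-loop home use |
| Closed Loop trial-period criteria | G.7, I | See below |
| Average SMBG above 4.5/day, with random data, to continue | B (Visit 5) | During closed-loop home use |
| Unreachable after alerts (discretionary) | G.8 | During closed-loop home use |

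How many of these feed the 1-week rule depends on three open points.

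- *Does the Pump-mode week count as intervention?* Section J describes the "interventions, subjects randomized to USS Virginia will participate in two training visits at a" monitored outpatient setting, with home use in Pump "mode followed by 4 weeks using AP at home in Closed Loop mode running USS Virginia". Section E also lists Pump mode under training and use. Both favour counting it. Section K's term pairs USS Virginia with the AP system, and Section A uses that term for the training that leads into closed loop, which leaves doubt. If the week counts, Visit 4 task failures are the main group below 1 week. If it does not, the first four rows all come before any closed-loop home use.
- *Is Visit 5 combined with Visit 4?* Section B allows it. Visit 5 tasks could then be judged before any home use.
- *Is the trial period repeated?* Section G.7 leaves this to the investigator. A subject not offered a repeat could end after 3–5 closed-loop days. One who repeats has 2 × 3 = 6 to 2 × 5 = 10 days, on either side of 7.

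**3. Size, on assumed inputs.** The documents give no failure rate for these criteria. The loss of about 40% combines screen failure, withdrawal and drop-out. They also give no link between failing a criterion and LBGI, and Section L names no test for LBGI.

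Let a share f of closed-loop subjects be left out, with mean LBGI δ SD higher (worse) than those retained, and nobody left out of the control arm. Then

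mean(all) = (1 − f) × mean(retained) + f × mean(left out), so mean(retained) − mean(all) = −f × δ.

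Lower LBGI is better, so the bias is f × δ SD in favour of closed loop. Assume no true effect, 44 / 2 = 22 per arm and a two-sided 5% two-sample t-test (df = 42). The non-centrality is f × δ / √(2/22).

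| Bias f × δ | Example | Non-centrality | False positives for closed loop | For control |
|---|---|---|---|---|
| 0 | δ = 0 | 0 | 2.5% | 2.5% |
| 0.025 | f = 5%, δ = 0.5 | 0.083 | 3.0% | 2.1% |
| 0.05 | f = 10%, δ = 0.5 | 0.166 | 3.6% | 1.7% |
| 0.10 | f = 20%, δ = 0.5 | 0.332 | 5.1% | 1.1% |
| 0.20 | f = 20%, δ = 1.0 | 0.663 | 9.5% | 0.5% |

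Negative δ gives the same sizes against closed loop. The smaller values of f fit the reading in which the Pump-mode week counts.

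**The case against.** The best defence is that nothing here orders an exclusion. Section K speaks of a general rule under a heading about success criteria, and could be meant as a per-protocol screen. Section I says that a subject may be replaced, which need not mean removed, and that available data will be used. The 20% allowance makes sense only if noncompliers stay in. Subjects who withdraw after more than 1 week are asked to attend Visit 6, so some outcomes after stopping are collected. For an early stopper, the last week of intervention has an ordinary meaning: the last week received.

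Much of this stands. A reader might infer that the plan abandons ITT, or that closed-loop failures will be dropped and the result biased in favour of closed loop. The documents do not support either: the wording is permissive, and nothing shows who fails or how their LBGI compares. Nor do they support the view that every device criterion falls before the 1-week mark, or that a trial-period failure always comes after 6–10 days.

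The illustration may also overstate the problem. It sets control-arm exclusions to zero although the 1-week rule covers both arms. The arms are matched on LBGI and the endpoint is taken against baseline, so differences of 0.5 to 1.0 SD may be less plausible.

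The conflict remains. Section K is not confined to the per-protocol analysis, no section defines the ITT set, and Section I does not say whether a replaced subject is still analysed.

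**Conclusion.** The concern holds as a conflict between Section L and Sections K and I. The text permits randomised subjects to be left out of the primary analysis on grounds that arise after randomisation, and device and task removal is stated for one arm only. Subjects who fail the tasks at the first Visit 4 fall below 1 week on any reading. How many others do depends on the three open points above.

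The size and direction of any bias cannot be determined from the documents. The figures, such as 0.05 SD and 3.6% against 2.5%, rest on assumed f and δ, no control-arm exclusions, equal arms of 22 and a t-test. If those left out do not differ from those retained, there is no bias.

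This should be fixed before the analysis: the population for the primary comparison is left to discretion, and the remedy is cheap.

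**What to change.** 1. State that the primary (ITT) set is all randomised subjects, analysed as allocated. Confine the 1-week rule and the device-use thresholds to the per-protocol set, and say there whether Pump-mode time counts.
2. State that replaced subjects stay in the ITT set and that replacements are additional.
3. Define the primary outcome week for early stoppers from CGM already collected, for example the last available week after randomisation. Downloads are planned after the Pump-mode week, at weeks 2 and 4 of closed loop, and at weeks 2 and 5 for controls. Treat subjects with no such week as missing.
4. Add a sensitivity analysis that shifts missing LBGI in both directions, and report losses by arm and by criterion.

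Leave all device criteria, stopping rules and Visit 6 eligibility as stated. Further CGM after stopping is optional and not part of this fix.

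The cost is wording, a little analysis, and the dilution that any ITT analysis carries. Under a two-sample t-test, an effect with 80% power at 36 / 2 = 18 per arm is 0.961 SD. If 10% of closed-loop subjects get no benefit it becomes 0.9 × 0.961 = 0.865 SD, with about 80% power at 22 per arm; at 20% it becomes 0.769 SD, with about 70%. An effect with 90% power at 18 per arm (1.112 SD) keeps about 90% and 82%.

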48 versus sensor-augmented pump (SAP) therapy for hypoglycemia prevention in subjects with
49 type 1 diabetes and hypoglycemia unawareness and/or risk for hypoglycemia.

[figure not shown]
50 Subjects: We will recruit up to 85 subjects aged 12-70 years old with type 1 diabetes
51 for at least the past 1 year, on insulin for at least the past 1 year, and on insulin pump
52 therapy for at least the past 6 months to achieve a goal of 44 completed subjects.

53 Subjects will be recruited at two clinical sites: University of Virginia and Stanford
54 University.

55 Procedure: Figure 1 below presents the overall flow of the study.

56

Figure 1: Study flow diagram

Visit 1: Screening 1 Visit. A meter ± CGM download will be performed to evaluate subject

60 eligibility (i.e. Average Daily Risk Range [ADRR] >40 or LBGI >2.5 from SMBG data or
61 LBGI >1.1 from 1 week of CGM data within the prior 3 weeks) and to determine pre-study
62 CGM use in the prior 4 weeks (active [CGM use \geq 5 days/week] or no CGM use). Baseline
63 HbA1c, hypoglycemia symptom awareness (presence of adrenergic symptoms at BG 60
64 mg/dL) and hypoglycemia questionnaires (Clarke Hypoglycemia Perception Awareness and
65 Fear of Hypoglycemia – APPENDIX A-5) will be assessed. Those subjects that qualify will
66 be trained to use the study glucometer and CGM in blinded mode and complete 1 week of
67 baseline blinded CGM and SMBG at least 4 times daily.

68

69 **Visit 2: Screening 2 Visit.** The blinded CGM will be downloaded and if review of the data
70 shows that the CGM was functional >80% of the time and the subject has confirmed risk of
71 hypoglycemia with LBGI >1.1 (#2) (per 1 week of blinded CGM), the subject will be
72 randomized to USS Virginia AP system experimental treatment or Sensor-Augmented Pump
73 Therapy control treatment and proceed to Visit 3. The experimental and control groups will
74 be matched for LBGI and pre-study CGM use. The study glucometer will be downloaded
75 and assessed for average SMBG/day and randomness of data. Subjects with average SMBG
76 <3.5/day and/or poor randomness of SMBG testing will be reminded of SMBG requirements
77 4-6 times daily (pre-meal, bedtime, before driving, before exercise, and as indicated). CGM
78 data collection period may be repeated.

79

80 **Visit 3: 8 hr Inpatient Assessment of Hypoglycemia Counterregulation and Symptom**
81 **Awareness.** The subjects will undergo hypoglycemia induction via a previously validated

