113 There will be an initial 3-5 day trial of the system at home in Closed Loop mode during
114 which, the subject will receive daily contact from study staff and remote monitoring
115 automated alerts will be in place. Study staff will also check the number of SMBG tests
116 entered on the AP system and will remind the subject to perform 4-6 SMBG daily. Study
117 staff will then determine whether additional training and practice is needed and whether the
118 subject will repeat all or portions of Visit 5 and 3-5 days of the AP system home use (up to 1
119 time) or proceed with the remainder of the 4 weeks of the system Closed Loop home use.
120 During the 4 weeks of home use, study staff will continue to contact the subject (daily for
121 the first 5 days, then weekly) to answer any questions and enquire about any device
122 complaints, adverse events, and whether the adverse event was related to the AP system use.
123 Study staff will check the number of SMBG entered on the AP system daily and contact the
124 subject if <4 SMBG are observed on any day. The subject's CGM data and meter data will
125 be collected at week 2 and week 4. Subjects will be required to have average SMBG
126 >4.5/day and random SMBG data to continue.

127

128 **Visit 6: 8 hr Inpatient Assessment of Hypoglycemia Counterregulation and Symptom**
129 **Awareness.** Within approximately one week of completing either USS Virginia or sensor-
130 augmented pump therapy at home, the subjects will undergo a final hypoglycemia induction
131 using the home pump therapy with frequently sampled YSI glucose levels. Hypoglycemia
132 counterregulation and symptoms will be assessed by epinephrine levels and hypoglycemia
133 symptom scoring as the BG is decreased from 100-150 mg/dL to <60 mg/dL. Post-
134 intervention HbA1c, and hypoglycemia questionnaires, and a DiAs Usability questionnaire
135 (DiAs users only) will be completed. If a subject completes more than 1 week of either USS
136 Virginia or sensor-augmented pump therapy and subsequently withdraws from the study
137 intervention, they will be asked to complete Visit 6 within one week of discontinuing the
138 intervention.

139

C. Pilot subjects

140 Each site will study two initial Pilot subjects: one aged 21-65 years old and one aged 15-20
141 years old. The Pilot subjects and their respective diabetes care partners will be used to test
142 the adequacy of the AP system training period and the system performance (in Pump mode)

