210 response measured in a hospital setting), restoration of hypoglycemia awareness,
211 and reduced fear of hypoglycemia.

212 213 **Primary Specific Aim:**

214 Reduction in hypoglycemia during the study on USS Virginia versus SAP as assessed by:

- 215 • LBGI from CGM during 1 week of baseline blinded use versus during the last week
216 of intervention.

217 218 **Secondary Specific Aims:**

219 Reduction in hypoglycemia during the study on USS Virginia versus SAP as assessed by:

- 220 • CGM time <70 mg/dL and <50 mg/dL by retrofitted CGM and SMBG trace during a
 221 24 hour period and the overnight period (11PM – 7AM) from 1 week of baseline
 222 blinded use versus the last week of intervention.
 223

224 Improvement in counterregulatory response to hypoglycemia at baseline versus follow-up as
 225 assessed by:

- 226 • Peak epinephrine
 227 • Epinephrine area under the curve (AUC)
 228 • Epinephrine increase over baseline
 229

230 Improvement in hypoglycemia awareness at baseline versus follow-up as assessed by:

- 231 • Hypoglycemia symptom ratings
 232 • Clarke Hypoglycemia Perception Awareness and Fear of Hypoglycemia scores
 233

234 Improvement in glycemic control at baseline versus the last week of intervention as assessed
 235 by:

- 236 • Time within target (70-180 mg/dL) over a 24 hour period.
 237 • Time within target (80-140 mg/dL) in the overnight period (11PM – 7AM)
 238 • Distribution of wake-up glucose levels at 7AM
 239

240 Sample size determination is based on literature data (#3) and on results from our previous
 241 studies of hypoglycemia unawareness (#4)**Error! Reference source not found..** We
 242 estimate, conservatively, that the effect size of using the AP system+USS Virginia vs. CGM
 243 in terms of restoration of epinephrine response will be moderate ~0.35. Power calculations
 244 assuming $\alpha=0.05$, and power of 80% yield a required sample size of N=36 (using G*Power
 245 3 software [#5]). With this sample size, the power for finding significant effects on
 246 frequency and extent of hypoglycemia (Low BG Index [#6]) exceeds 0.9. Assuming a
 247 proportion of noncompliance R=20% for Intention-to-Treat (ITT) analysis (#7), 44
 248 completed subjects will adequately address the specific aims of this study. Per-protocol
 249 analysis will also be performed. In order to achieve 44 completed subjects, up to 70 subjects
 250 may sign consent given an expected screen failure, withdrawal and drop-out rate of ~40%

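### The step from N=36 to 44 completers replaces lost subjects but does not offset ITT dilution: if noncompliers gain nothing, power for the epinephrine effect at 44 is about 70–73%, not 80%

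*Combined protocol and SAP*

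**What the plan says.** Sections D and L carry the same sample-size paragraph. It takes an effect size of about 0.35 for restoration of the epinephrine response, α = 0.05, "and power of 80% yield a required sample size of N=36 (using G*Power 3" software. At that N, power for "frequency and extent of hypoglycemia (Low BG Index [#6]) exceeds 0.9. Assuming a" noncompliance proportion then follows: "proportion of noncompliance R=20% for Intention-to-Treat (ITT) analysis (#7), 44" "completed subjects will adequately address the specific aims of this study. Per-protocol" analysis is named as a further analysis.

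Losses before completion have their own allowance: "In order to achieve 44 completed subjects, up to 70 subjects" may consent, given about 40% screen failure, withdrawal and drop-out. Section B has a different ceiling: "We will recruit up to 85 subjects aged 12-70 years old with type 1 diabetes".

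On who is analysed, Section K says that a subject's "data will be considered useful for data analysis if the" subject completes at least 1 week of the intervention. Section B (Visit 6) says of subjects who stop after more than 1 week that "they will be asked to complete Visit 6 within one week of discontinuing the" intervention.

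The plan shows no formula for going from 36 to 44, does not define noncompliance, and does not say how much benefit a noncomplier is assumed to keep.

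**The concern.** R=20% is introduced for the ITT analysis, while screen failure, withdrawal and drop-out are covered by the separate 40%. The natural reading is therefore that R describes noncompliance among the 44. In an ITT analysis those subjects stay in their randomised arm and pull the two means together. Sample size then has to grow with the inverse square of the diluted effect. A linear allowance grows too slowly. It keeps the number of compliers near 36 (44 × 0.8 = 35.2), which suits a per-protocol analysis.

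At stake is the statement that 44 is adequate for the specific aims. A reader will take it to mean a 20% chance of missing the assumed epinephrine effect in ITT. Under the dilution above, that chance is nearer 30%.

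**Working it through.** **Inputs from Sections D and L.** N = 36 for 80% power; α = 0.05; R = 0.20; target 44; LBGI power above 0.9 at N = 36. **Assumed, because not stated:** two-sided test, 1:1 allocation, ITT set equal to the 44.

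**1. Reproducing 44.** 36 × (1 + 0.20) = 43.2, which is 44 when rounded up. 36/(1 − 0.20) = 45. Both are linear.

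**2. Reproducing 36.** A repeated-measures ANOVA with two groups, two measurements, correlation 0 and f = 0.35 has noncentrality 2 × 36 × 0.35² = 8.82 on 1 and 34 df, and power 0.823. A regression F test with f² = 0.35 and three predictors gives 0.810. A two-sample t-test with d = 0.35 would need 260. So 36 can be reached, but only with settings the plan does not give.

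**3. Dilution.** If noncompliers keep a share k of the benefit, the ITT difference is multiplied by g = 0.80 + 0.20k. Required N is 36/g². Approximate power at N is Φ[(z₀.₉₇₅ + z₀.₈₀) × √(N/36) × g − z₀.₉₇₅].

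For k = 0 and N = 44: Φ(2.802 × 1.1055 × 0.80 − 1.960) = Φ(0.518) = 0.698. The noncentral t, with the effect set to give 80% power at N = 36, gives:

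| Benefit kept by noncompliers | g | 36/g² | Power at 44 |
|---|---|---|---|
| none | 0.80 | 56.25, i.e. 57 | 0.703 |
| 25% | 0.85 | 49.8, i.e. 50 | 0.754 |
| 50% | 0.90 | 44.4, i.e. 45 | 0.800 |

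Break-even at 44 is g = √(36/44) = 0.9045, so k = (0.9045 − 0.80)/0.20 = 0.52. With no benefit in noncompliers, 44 holds 80% power only up to R = 1 − 0.9045, about 9.5%.

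**4. Dependence on the test behind 36.** Both models in step 2 start slightly above 80%, so they are a little more forgiving. With k = 0:

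- Repeated measures: f = 0.35 × 0.80 = 0.28, and power at 44 is 0.728. At 52 it is 0.80 to two decimals; 53 is the first N strictly above.
- Regression: power at 44 is 0.708, and 53 are needed.

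A one-sided two-sample test gives 0.713 at 44. Across these versions, power at 44 is about 70–73%, and full offset takes about 52–57 analysed subjects.

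These formulas ignore the extra spread created by mixing compliers and noncompliers in one arm. A simulation with 20% zero-benefit noncompliers in the AP arm only gave 0.672 at 22 per arm, so 70–73% is not the pessimistic end.

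**5. LBGI.** With the same dilution at k = 0, a power of exactly 0.90 at N = 36 becomes 0.82 at N = 44, and 0.95 becomes 0.89. Power at N = 36 would have to be about 0.954 for it to stay above 0.9 at 44.

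**The case against.** The strongest reply is that the 44 need not be the ITT set. It is a count of completed subjects, and the evidence that noncompliers are kept (Visit 6 after early discontinuation, data counted after 1 week, and the statement in Section I that available data will be used) concerns people who did not complete. Section I also stops AP-arm subjects with low system use, so noncompliers may largely become non-completers. If the 44 are the compliant 80% of a larger set, that set is 44/0.8 = 55. Diluted power at 55 is 0.799, and LBGI at 0.90 stays at about 0.90. The consents fit too: (70 − 44)/70 = 37%, close to the stated 40%.

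This reading is arithmetically possible, but the plan describes no set of 55. It ties the 44 itself to the ITT allowance and counts withdrawal and drop-out in the separate 40%. What stands is that the plan must say whether withdrawn subjects are analysed on top of the 44.

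The reply also notes, correctly, that zero benefit is the extreme assumption, particularly for an AP subject who has met the system-use requirements. At half the benefit, 44 is about right. The plan does not say that it assumes this.

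**Conclusion.** The point holds conditionally. The step to 44 does not offset dilution, so the stated adequacy for ITT at R=20% is not delivered on the natural reading. If the ITT set is the 44 and noncompliers gain nothing, power for the assumed epinephrine effect is about 70–73%. It is about 75% with a quarter of the benefit kept and about 80% with about half.

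A reader might infer three stronger conclusions that the documents do not support:

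- **The trial needs 57 completers.** That figure requires zero benefit, all noncompliers inside the 44, and a test with exactly 80% power at 36. The repeated-measures model that returns 36 needs only about 52–53.
- **The primary endpoint is underpowered.** The plan gives only a lower bound for LBGI power at N=36. Even a starting value of exactly 0.90 leaves about 0.82. Power above 0.9 is not assured after dilution, but no shortfall is shown.
- **N=36 is wrong.** It can be reproduced; its inputs are simply not reported.

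**What to change.** Keep 44. In Sections D and L, replace the sentence that introduces R=20% with:

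> *N=36 assumes full compliance. With R=20% noncompliance and no benefit in noncompliers, 44 analysed subjects give about 70% ITT power for the assumed epinephrine effect (about 80% if noncompliers keep half the benefit).*

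Then restate the LBGI power on the same basis, with the effect assumed for it. State whether withdrawn subjects with at least 1 week of intervention are analysed in addition to the 44. Giving the G*Power inputs behind 0.35 (metric, test, sidedness, allocation, correlation) would let a reader settle where in the 70–73% range the plan lies.

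The cost is wording in two sections and a lower stated ITT power. No added enrolment is proposed. Raising the target to 57 would imply 57/0.6 = 95 consents at the plan's 40% loss, above both stated ceilings (70 and 85), and would oversize the trial if withdrawn subjects are in fact analysed on top of the 44.
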